### **Analyses:**

An overview table will show the number and percentage of subjects with at least one TEAE for several categories (e.g. AEs, serious AEs, and fatal AEs).

For each particular TEAE, the percentage and frequency of subjects who experience at least 1 occurrence of the given event will be tabulated. All adverse events will be sorted by incidence based on all subjects (column not provided). The following TEAEs tables will be included in the analysis:

- All TEAEs
- Serious TEAEs
- At least grade 3 TEAEs
- At least grade 2 TEAEs and related
- TEAEs leading to discontinuation
- Related TEAEs
- TEAEs in at least 2 subjects in total
- Events of special interest

All AEs, any serious TEAE, related TEAE, TEAE leading to death, TEAE leading to discontinuation, TEAE of at least grade 3, or ESI will be separately listed. Listings will include all information collected on the Adverse Event CRF pages (e.g. information on time of onset, duration of events, time of resolution, concomitant therapies and relationship to study treatment.)

---

For subjects reporting rash a listing with specific grade will be provided (see rash specific grade in **APPENDIX** ) and Rash Questionnaire will be tabulated by study treatment group and overall.

## 6.2. Clinical Laboratory Tests

Laboratory data from the central laboratory will be summarized by type of laboratory test. The different categories and tests used in the analysis are listed in table 6. The tests will be allocated to the categories in the table. The analysis of laboratory data will be analyzed on Standard International converted values only (LBSTREN/LBSTRESU) except lab parameter ‘GFR from Creatinine Adjusted for BSA” should be reported in Original Units (mL/min/1.73m^2).

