A urine sample must be provided for urinalysis. Specific gravity, pH, glucose, protein, blood, ketones, bilirubin, urobilinogen, nitrite, and leukocyte esterase will be determined using dipstick. In case of positive dipstick results, the sediment will be examined microscopically for RBCs, WBCs, and epithelial cells and an additional examination will be performed on the positive urinary parameter (eg, quantification as applicable). Crystals, casts and bacteria will only be reported if they are present.

- At screening, a serum pregnancy test will be performed for women of childbearing potential.
- At screening, an FSH test will be performed for postmenopausal women.

- At time points as indicated in the **TIME AND EVENTS SCHEDULE**, a urine pregnancy test will be performed (women of childbearing potential only).
- At screening, a HIV-1 and -2 test, and hepatitis A, B, C, D, and E tests will be performed.
- At screening and time points as indicated in the **TIME AND EVENTS SCHEDULE**, tests will be performed for HBsAg, HBeAg, HBcAg, and anti-HBs and anti-HBe antibodies.
- At screening and time points as indicated in the **TIME AND EVENTS SCHEDULE**, determination of coagulation parameters will be performed. INR will be calculated by the central laboratory.
- At screening, alpha-fetoprotein will be measured.

In case of **rash**, blood samples (mandatory blood sample for safety in case of Grade 3 or Grade 4 rash and at the discretion of the investigator in case of Grade 1 or Grade 2 rash) need to be taken for safety laboratory testing, and are to be processed by the local laboratory. These samples need to be taken at unscheduled visits as described in [Attachment 3](#). The following parameters need to be tested: AST, ALT, erythrocyte sedimentation rate, creatinine, and a complete blood cell count (including hemoglobin, hematocrit, RBC count, WBC count, neutrophils, lymphocytes, monocytes, eosinophils, basophils, and platelet count).

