#### **Clinical Laboratory Tests**

Laboratory data will be summarized by type of laboratory test. Descriptive statistics (n, mean, standard error [SE], SD, 95% CI, minimum, median, and maximum) of the actual values and changes from baseline per time point will be tabulated per treatment.

The laboratory abnormalities will be determined according to the criteria specified in the DAIDS Toxicity Grading Scale and in accordance with the normal ranges of the clinical laboratory if no gradings are available.

Based on current data review, for this study cholesterol increased is considered a laboratory abnormality of interest.

The percentage of the subjects who experience (worst) laboratory abnormalities will be tabulated by study treatment.

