**Table 6: Laboratory Parameters to Be Summarized**

Category	Abnormality	SDTM LBTESTCD	Grading system
General biochemistry	Alpha-1 Acid Glycoprotein	A1AGLP	Abnormalities
	Alpha Fetoprotein	AFP	Abnormalities
	Albumin	ALB	DAIDS
	Amylase	AMYLASE	DAIDS
	Amylase, Pancreatic	AMYLASEP	DAIDS
	Bicarbonate	BICARB	DAIDS
	Calcium	CA	DAIDS
	Creatine Kinase	CK	DAIDS
	Chloride	CL	Abnormalities
	Creatinine	CREAT	DAIDS
	C Reactive Protein	CRP	Abnormalities
	Follicle Stimulating Hormone	FSH	NAP
	GFR from Creatinine Adjusted for BSA	GFRBSCRT	DAIDS
	Choriogonadotropin Beta	HCG	NAP
	Potassium	K	DAIDS
	Lipase	LIPASET	DAIDS
	Magnesium	MG	DAIDS
	Phosphate	PHOS	DAIDS
	Protein	PROT	Abnormalities
	Sodium	SODIUM	DAIDS
Urate	URATE	DAIDS	
Urea Nitrogen	UREAN	Abnormalities	
General hematology	Hematocrit	HCT	Abnormalities

Hemoglobin	HGB	DAIDS	
Hypochromic RBC (RBC)	HPORBC	Abnormalities	
Mean Corpuscular hemoglobin	MCH	Abnormalities	
MCH concentration	MCHC	Abnormalities	
Mean Corpuscular volume	MCV	Abnormalities	
Platelet count	PLAT	DAIDS	
Erythrocytes	RBC	Abnormalities	
Leukocytes	WBC	DAIDS	
Hematology coagulation	Activated Partial Thromboplastin Time	APTT	DAIDS
	Fibrinogen	FIBRINO	DAIDS
	Prothrombin Intl. Normalized Ratio	INR	NAP
	Prothrombin Time	PT	DAIDS
Hematology different counts	Basophils	BASO	Abnormalities
	Basophils/Leukocytes	BASOLE	Abnormalities
	Eosinophils	EOS	Abnormalities
	Eosinophils/Leukocytes	EOSLE	Abnormalities
	Lymphocytes	LYM	Abnormalities
	Lymphocytes/Leukocytes	LYMLE	Abnormalities
	Monocytes	MONO	Abnormalities
	Monocytes/Leukocytes	MONOLE	Abnormalities
	Neutrophils and Precursors	NEUTPR	DAIDS
	Neutrophils, Segmented	NEUTSG	Abnormalities
	Neutrophils, Segmented/Leukocytes	NEUTSGLE	Abnormalities
Hepatic parameters	Alkaline phosphokinase	ALP	DAIDS
	Alanine Aminotransferase	ALT	DAIDS
	Aspartate Aminotransferase	AST	DAIDS
	Direct Bilirubin	BILDIR	Abnormalities
	Bilirubin	BILI	DAIDS
	Indirect Bilirubin	BILIND	Abnormalities
	Gamma glutamyl transferase	GGT	Abnormalities
	Lactate Dehydrogenase	LDH	Abnormalities
Lipids and glucose	Cholesterol	CHOL	DAIDS
	Glucose	GLUC	DAIDS
	HDL Cholesterol	HDL	Abnormalities
	LDL Cholesterol	LDL	DAIDS
	Triglycerides	TRIG	DAIDS
Urinalysis	Urine Pregnancy	HCG	NAP
	Protein	PROT	DAIDS
	Glucose	GLUC	DAIDS
	Bilirubin	BILI	Abnormalities
	pH	PH	Abnormalities

	Specific Gravity	SPGRAV	Abnormalities
	Ketones	KETONES	Abnormalities
	Urobilinogen	UROBIL	NAP
	Nitrite	NITRITE	Abnormalities
	Leukocyte Esterase	LEUKASE	Abnormalities

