### Toxicity grades and abnormalities for laboratory parameters:

The laboratory abnormalities will be determined according to the criteria specified in the Division of AIDS (DAIDS) Toxicity Grading Scale. In case different grades are available for fasted/non-fasted results, the results are assumed to be taken in the condition as specified in the protocol (i.e. not necessarily according to possible remarks indicating a deviation to this). In case no toxicity grades are defined for a laboratory test, then non-graded abnormalities (high/low vs. normal range) will be used. The tests with toxicity grades and abnormalities have been summarized in table 6. Toxicity grades according to DAIDS will be derived for urinary protein and urinary glucose although these are categorical test (see table 7).

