### **Worst grade/abnormality determination:**

A worst-case analysis time point will be created for parameters for which abnormalities and/or toxicity grades are defined to summarise values considered as the worst-case. For abnormalities it is derived per parameter and in case both the lowest and the highest values are considered abnormal, a subject can have two worst-case analysis visits for a same parameter within each phase/period. For toxicity grades the worst-case is the value associated to the highest toxicity grade and is derived per parameter and toxicity direction (hypo / hyper). Worst-case will be derived within each phase/period, including unscheduled assessments.

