### **Analyses:**

- Descriptive statistics of the actual values and the change from baseline per parameter over time according to the specification described in section 2.6 will be included.
- A cross-tabulation of the worst toxicity grades versus baseline parameter and per analysis phase/period will be presented including also the number of subjects per worst grade, the number of subjects with treatment emergent worst grades per grade and the cumulative number of subjects.
- A cross-tabulation of the worst abnormalities versus baseline per parameter and analysis phase/period will be presented including also the number of subjects per abnormality, the number of subjects with treatment emergent abnormalities per abnormality.
- A tabulation of percentage and number of the subjects who have treatment-emergent worst toxicity grades per parameter and analysis phase/period will be included.

---

- A tabulation of percentage and number of the subjects who have treatment-emergent worst abnormalities per parameter and analysis phase/period will be included.
- A listing including all parameters with at least one treatment-emergent toxicity or abnormality per subject (exclusion of urinalysis) is provided.
- All results of the hepatic parameters per subject for subjects with at least one treatment-emergent abnormality/toxicity within these hepatic parameter results is included in a listing.
- A listing including all parameters with at least one grade 3 treatment-emergent toxicity per subject (exclusion of urinalysis) is presented.
- A listing with abnormal urinalysis results and a listing including all urinalysis data will be provided.
- The actual values over time are plotted per the laboratory parameter. Each line will represent one subject.
- Mean (+/- SE) plots of the actual values for alanine transferase will be presented.
- Mean (+/- SE) plots of the change from baseline for alanine transferase will be presented.

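### SAP Table 6 omits urine blood, the only one of ten protocol dipstick parameters left out, so dipstick haematuria not reported as an adverse event gets no count by arm

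*SAP*

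**What the plan says.** Protocol Section 9.9 (Clinical Laboratory Tests, Urinalysis) sets out the dipstick panel: "Specific gravity, pH, glucose, protein, blood, ketones, bilirubin, urobilinogen, nitrite, and leukocyte esterase will be determined using dipstick". A positive dipstick leads to sediment microscopy, including red cells. The Time and Events Schedule places urinalysis at every treatment visit. Protocol Section 11.10 then states in general terms: "The percentage of the subjects who experience (worst) laboratory abnormalities will be tabulated by study treatment".

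SAP Section 6.2 fixes the scope of the laboratory analysis: "The different categories and tests used in the analysis are listed in table 6". That table is titled "Laboratory Parameters to Be Summarized". Its urinalysis block holds urine pregnancy, protein, glucose, bilirubin, pH, specific gravity, ketones, urobilinogen, nitrite and leukocyte esterase. There is no blood row. The same section says that the tests carrying toxicity grades or abnormalities are those in Table 6.

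The displays by arm depend on such a rule. On worst cases the SAP says: "A worst-case analysis time point will be created for parameters for which abnormalities and/or toxicity grades are defined". On counts: "A tabulation of percentage and number of the subjects who have treatment-emergent worst abnormalities per parameter and analysis phase/period will be included". For urine it adds by-subject output: "A listing with abnormal urinalysis results and a listing including all urinalysis data will be provided".

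**The concern.** A safety result that the protocol collects at every treatment visit drops out of the comparative tables because of one missing row. A dipstick finding of blood that the investigator does not consider clinically relevant would appear only in listings. Anyone wanting to compare arms would have to count it by hand.

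The parameter bears on this trial. Protocol Section 1.2 names the kidney as a target organ for both JNJ-56136379 and TDF, and traces the rat nephropathy to calculi in the lower urinary tract. Protocol Section 1.3.5 gives that nephropathy as the reason for monitoring renal safety parameters. What is at stake is the completeness of the renal safety display. No efficacy conclusion and no planned decision is affected.

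**Working it through.** The plan gives no figure to reproduce. The check compares two lists and then follows the SAP's rules.

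**Step 1: the lists.** Protocol Section 9.9 against the urinalysis block of SAP Table 6:

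| Dipstick parameter (protocol) | SAP Table 6 grading system |
|---|---|
| Protein | DAIDS |
| Glucose | DAIDS |
| Bilirubin | Abnormalities |
| pH | Abnormalities |
| Specific gravity | Abnormalities |
| Ketones | Abnormalities |
| Nitrite | Abnormalities |
| Leukocyte esterase | Abnormalities |
| Urobilinogen | NAP |
| Blood | not listed |

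Measured: 10. Listed: 9. Missing: 10 − 9 = 1 (blood). With a grading or abnormality rule: 2 DAIDS + 6 Abnormalities = 8 of 10 (80%). Without a rule: urobilinogen (listed, NAP) and blood (absent).

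**Step 2: could another rule bring blood in?**
- SAP Section 6.2 has a fallback of high/low against the normal range for tests without toxicity grades. It is generic, does not name blood, and sits within an analysis already limited to Table 6.
- Sediment red cells have no urinalysis row either. The erythrocyte row in Table 6 belongs to general hematology.
- The listing of treatment-emergent toxicities and abnormalities, and the grade 3 listing, both exclude urinalysis.

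So the two urinalysis listings are the only planned laboratory output in which dipstick blood appears.

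**Step 3: how much data is involved.** Planned numbers are from Protocol Section 3.1:
- JNJ-56136379 arms: 2 parts × (30 + 30 + 30) = 180.
- Placebo+NA arms: 2 parts × (10 + 10) = 40.
- Total: 180 + 40 = 220.
- Post-baseline urinalyses to Week 24 (Weeks 1, 2, 4, 8, 12, 16, 20, 24): 8 per subject, so 220 × 8 = 1,760 planned blood results.

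Fewer will occur in that window because Arm 1 was stopped early. Weeks 28 to 48 and follow-up add more.

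**Step 4: an illustration in subjects.** The documents give no haematuria rate. Assume that 2% to 10% of subjects in both groups have a treatment-emergent positive result:
- JNJ-56136379: 180 × 0.02 = 3.6, and 180 × 0.10 = 18.
- Placebo+NA: 40 × 0.02 = 0.8, and 40 × 0.10 = 4.

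Of these, only cases reported as adverse events would reach a table by arm.

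**The case against.** The case against giving this much weight is strong, and most of it stands.

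- **No specific promise is broken.** Protocol Section 11.10 speaks of laboratory abnormalities in general, and Section 11 calls itself a general description. The study is exploratory, without formal hypothesis testing. The SAP makes other analyte-level choices: urobilinogen and INR are listed but marked NAP.
- **There are other safeguards.** All urinalysis data are listed, and clinically relevant changes must be entered as adverse events and so reach the TEAE tables. Confirmed grade 3 or 4 urinalysis abnormalities have their own management rules, including stopping JNJ-56136379 in defined cases. What goes uncounted is therefore mainly lower-grade blood judged not clinically relevant.
- **The renal rationale is qualified.** Protocol Section 1.2 calls the rat finding probably species-specific and not a direct effect on the kidney, reports no kidney findings in dogs, and expects no additive toxicity with TDF. Creatinine, eGFR and urine protein are all DAIDS-graded in Table 6.
- **The illustration shows no contrast.** Its rates are assumed, and equal in both groups. The missing table counts subjects, so 1,760 results describes the data collected, not the loss.

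These points keep the matter minor but do not remove it. The adverse event route depends on the investigator's judgement of relevance, which in the open-label Arms 1 and 6 is made knowing the treatment. A laboratory count does not depend on that judgement. The SAP allows minor changes to table design, which makes the correction easy but does not specify it.

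One caution remains. Table 6 runs over a page break within the urinalysis block, so the absence of the row should be confirmed in the issued SAP. Nothing in the text suggests that a row was lost.

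**Conclusion.** The point holds as a low-cost improvement. Table 6 carries nine of the ten dipstick parameters and omits blood alone, without a stated reason. Read literally, SAP Section 6.2 then provides no shift from baseline and no treatment-emergent count by arm for dipstick blood. Subject listings and the adverse event route remain.

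The conclusion rests on reading Table 6 as the complete list of tests analysed, as Section 6.2 and the table's title indicate, and on reading the worst-case rule as covering only parameters with a defined grade or abnormality. The SAP does not use the word only, but no other reading gives blood a rule. The 2% to 10% rates are assumptions and the conclusion does not depend on them. Sample size, power and error rates are unaffected.

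**What to change.** Add urine blood (dipstick) to the urinalysis block of SAP Table 6 with the grading system Abnormalities, positive versus negative, or DAIDS if a grade applies. State how a trace result is classified. Table 7 cannot settle this by analogy, because it puts trace at grade 0 for protein and grade 1 for glucose.

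No new method is needed. Nitrite, ketones and leukocyte esterase are already handled as dipstick abnormalities, and for two other parameters the SAP already says: "Toxicity grades according to DAIDS will be derived for urinary protein and urinary glucose although these are categorical test". Those with a rule would rise from 8 to 9 of 10, with urobilinogen remaining NAP.

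The cost is one row in Table 6 and one extra row in the matching worst-abnormality and treatment-emergent tables. No further data are collected.

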**Table 6: Laboratory Parameters to Be Summarized**

Category	Abnormality	SDTM LBTESTCD	Grading system
General biochemistry	Alpha-1 Acid Glycoprotein	A1AGLP	Abnormalities
	Alpha Fetoprotein	AFP	Abnormalities
	Albumin	ALB	DAIDS
	Amylase	AMYLASE	DAIDS
	Amylase, Pancreatic	AMYLASEP	DAIDS
	Bicarbonate	BICARB	DAIDS
	Calcium	CA	DAIDS
	Creatine Kinase	CK	DAIDS
	Chloride	CL	Abnormalities
	Creatinine	CREAT	DAIDS
	C Reactive Protein	CRP	Abnormalities
	Follicle Stimulating Hormone	FSH	NAP
	GFR from Creatinine Adjusted for BSA	GFRBSCRT	DAIDS
	Choriogonadotropin Beta	HCG	NAP
	Potassium	K	DAIDS
	Lipase	LIPASET	DAIDS
	Magnesium	MG	DAIDS
	Phosphate	PHOS	DAIDS
	Protein	PROT	Abnormalities
	Sodium	SODIUM	DAIDS
Urate	URATE	DAIDS	
Urea Nitrogen	UREAN	Abnormalities	
General hematology	Hematocrit	HCT	Abnormalities

Hemoglobin	HGB	DAIDS	
Hypochromic RBC (RBC)	HPORBC	Abnormalities	
Mean Corpuscular hemoglobin	MCH	Abnormalities	
MCH concentration	MCHC	Abnormalities	
Mean Corpuscular volume	MCV	Abnormalities	
Platelet count	PLAT	DAIDS	
Erythrocytes	RBC	Abnormalities	
Leukocytes	WBC	DAIDS	
Hematology coagulation	Activated Partial Thromboplastin Time	APTT	DAIDS
	Fibrinogen	FIBRINO	DAIDS
	Prothrombin Intl. Normalized Ratio	INR	NAP
	Prothrombin Time	PT	DAIDS
Hematology different counts	Basophils	BASO	Abnormalities
	Basophils/Leukocytes	BASOLE	Abnormalities
	Eosinophils	EOS	Abnormalities
	Eosinophils/Leukocytes	EOSLE	Abnormalities
	Lymphocytes	LYM	Abnormalities
	Lymphocytes/Leukocytes	LYMLE	Abnormalities
	Monocytes	MONO	Abnormalities
	Monocytes/Leukocytes	MONOLE	Abnormalities
	Neutrophils and Precursors	NEUTPR	DAIDS
	Neutrophils, Segmented	NEUTSG	Abnormalities
	Neutrophils, Segmented/Leukocytes	NEUTSGLE	Abnormalities
Hepatic parameters	Alkaline phosphokinase	ALP	DAIDS
	Alanine Aminotransferase	ALT	DAIDS
	Aspartate Aminotransferase	AST	DAIDS
	Direct Bilirubin	BILDIR	Abnormalities
	Bilirubin	BILI	DAIDS
	Indirect Bilirubin	BILIND	Abnormalities
	Gamma glutamyl transferase	GGT	Abnormalities
	Lactate Dehydrogenase	LDH	Abnormalities
Lipids and glucose	Cholesterol	CHOL	DAIDS
	Glucose	GLUC	DAIDS
	HDL Cholesterol	HDL	Abnormalities
	LDL Cholesterol	LDL	DAIDS
	Triglycerides	TRIG	DAIDS
Urinalysis	Urine Pregnancy	HCG	NAP
	Protein	PROT	DAIDS
	Glucose	GLUC	DAIDS
	Bilirubin	BILI	Abnormalities
	pH	PH	Abnormalities

	Specific Gravity	SPGRAV	Abnormalities
	Ketones	KETONES	Abnormalities
	Urobilinogen	UROBIL	NAP
	Nitrite	NITRITE	Abnormalities
	Leukocyte Esterase	LEUKASE	Abnormalities
Immunology	Hepatitis A, B, C, D and E		

### Imputation rules:

Laboratory records with missing assessment date parts (any: day/month/year) will not be imputed.

In case continuous laboratory results are not numerically expressed, but as a character (e.g. 'less than 2', '>25'), these results will be numerically imputed –if possible– by adding or subtracting one precision unit to the provided value. This also applies to normal limits expressed as such.

Unless a parameter is clearly continuous as a whole (e.g. pH, specific gravity) no such imputations will be done for urinalysis parameters as these are usually character/categorical expressions.

### Toxicity grades and abnormalities for laboratory parameters:

The laboratory abnormalities will be determined according to the criteria specified in the Division of AIDS (DAIDS) Toxicity Grading Scale. In case different grades are available for fasted/non-fasted results, the results are assumed to be taken in the condition as specified in the protocol (i.e. not necessarily according to possible remarks indicating a deviation to this). In case no toxicity grades are defined for a laboratory test, then non-graded abnormalities (high/low vs. normal range) will be used. The tests with toxicity grades and abnormalities have been summarized in table 6. Toxicity grades according to DAIDS will be derived for urinary protein and urinary glucose although these are categorical test (see table 7).

**Table 7: urinary protein and urinary glucose according to DAIDS**

Parameter	Grade 0	Grade 1	Grade 2	Grade 3
Urinary protein	Normal, Negative, Trace	+1, 1+	+2, 2+	+3, 3+ (or higher)

---

Urinary glucose	Normal, Negative	Trace, +1, 1+	+2, 2+	+3, 3+ (or higher)
-----------------	---------------------	---------------	--------	--------------------

### **Treatment-emergent definition for toxicity grades and abnormalities:**

An assessment is treatment-emergent if the toxicity grade/abnormality worsened as compared to the grade/abnormality at baseline; this also includes the shift from abnormally high to abnormally low and vice-versa. Post-reference toxicities/abnormalities are always treatment-emergent with regard to missing toxicities/abnormalities at baseline. The abnormalities ‘Abnormally high’ and ‘Abnormally low’ are considered equally important.

### **Worst grade/abnormality determination:**

A worst-case analysis time point will be created for parameters for which abnormalities and/or toxicity grades are defined to summarise values considered as the worst-case. For abnormalities it is derived per parameter and in case both the lowest and the highest values are considered abnormal, a subject can have two worst-case analysis visits for a same parameter within each phase/period. For toxicity grades the worst-case is the value associated to the highest toxicity grade and is derived per parameter and toxicity direction (hypo / hyper). Worst-case will be derived within each phase/period, including unscheduled assessments.

